### 9.1.2 Sensitivity and Supporting Analyses

The primary analysis will be followed by two sensitivity analyses to investigate the impact of missing data on the treatment estimates. Additionally, a MAR mixed model will be reported for reference.

#### 9.1.2.1 ‘Other’ Dropouts as MNAR

This sensitivity analysis will be a repeat of the primary efficacy analysis, but including participants that have ‘other’ marked as the reason for drop out included with the dropouts reasons to be imputed under the MNAR assumption (imputed values based on the baseline distribution).

#### 9.1.2.2 All dropouts as MNAR

This sensitivity analysis will be a repeat of the primary efficacy analysis, but imputing all dropouts under the MNAR assumption with values based on the baseline distribution.

#### 9.1.2.3 MAR Mixed Model Repeated Measures

This analysis will be identical to the primary analysis, but will not include the MI stage described above.

### 9.1.3 Graphical Representations

The time course of response of the CAPS-5 total score will be presented graphically with time/weeks on the x-axis and the CAPS-5 total score on the y-axis. The means for each treatment group will be plotted over time.

The percent of participants reaching varying levels of improvement in CAPS-5 will be displayed in several manners. For each, the percent of participants will be out of all participants in the mITT population; thus, missing participants will be considered to have no improvement. All graphs will be produced with separate bars/lines for each treatment.

First, a continuous responder graph will be produced with percent improvement to Week 12 on the X-axis and the percent of participants achieving that level of improvement on the Y-axis. The X-axis will start at 0, so the Y intercept represents participants with any improvement; because the X-axis starts at zero and percentages are reported out of the mITT population, those with worsening/no improvement and those with missing data will be grouped together and their frequency represented by the Y intercept.

[figure not shown]
Secondly, a similar graph will be produced, but substituting the absolute change from baseline for percent improvement, again with X-axis starting at 0, so the Y intercept represents subject with any improvement; those with worsening/no improvement and those with missing data will be grouped together.

[figure not shown]
Additionally, a bar chart will be presented showing the percent of participants in 5-point groupings of Week 12 CAPS-5 scores. Percent of participants with missing data will be reported.

Finally, a bar chart will be presented showing the percent of participants in 5-point groupings of Week 12 change from baseline CAPS-5 scores. Those with worsening/no improvement and those with missing data will be presented as separate groups and the percent reported.

### 9.1.4 Exploratory Analyses of CAPS-5 scores

#### 9.1.4.1 Randomization honoring non-parametric combination of tests

9.1.4.2 14-item total CAPS-5 score

## 9.2 Secondary Efficacy Analysis

### 9.2.1 Continuous outcomes

The analyses of continuous secondary endpoints will be analyzed using an MMRM model identical to the primary endpoint, however, there will be no multiple imputation applied. These endpoints will include:

- CGI-S score.
- Change from baseline in SDS total.
- Change from baseline in participants' quality of sleep using the PROMIS Sleep Disturbance scale T-scores.
- CGI-I score
- Change from baseline in the disruption of work/school activities assessed using the SDS.
- Change from baseline in disruption of social life/ leisure activities assessed using the SDS.
- Change from baseline in the disruption of family life/home responsibilities assessed using the SDS.
- Change from baseline in CAPS-5 Arousal and Reactivity (Criterion E).
- Change from baseline in CAPS-5 Intrusion symptoms (Criterion B).
- Change from baseline in CAPS-5 Negative Cognition and Mood (Criterion D).
- Change from baseline in CAPS-5 Persistent Avoidance (Criterion C).
- Change from baseline in CAPS-5 Sleep Disturbance (item E-6).
- Mean PGIC score

- Change from baseline in CAPS-5 Reckless or Self-Destructive Behavior (item E-2).
- Changes from baseline in patient-rated Changes in Sexual Functioning Questionnaire Short-Form (CSFQ-14) in males and in females, analyzed separately
- Change from baseline in MADRS score.

The model will be changed to include the corresponding baseline value of the secondary endpoints instead of baseline CAPS-5. Randomized participants who have a baseline and at least one post-baseline assessment for the endpoint being analyzed will be included in the model. To estimate the difference between the treatment arms in CGI-I and PGIC scores (which do not have baseline assessments), the same method will be used, however, with the observed baseline response and associated interactions removed from the list of covariates. All visits will be included in the analysis. P-values from these comparisons will be considered nominal (conclusions from the sequential testing algorithm will be reported separately).

For each outcome, descriptive statistics (mean, SD, median, minimum and maximum) will be reported as well as LS means, standard error (SE) and p-values comparing the treatment and placebo arms at each visit. The time point of primary interest for all the above outcomes will be 12 weeks. In addition, for the SDS, the frequency of participants not working or attending school due to reasons unrelated to PTSD will be reported overall and within each visit.

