13.5. Safety Analyses

Safety will be assessed by:

- Adverse events and serious AEs throughout the entire duration of the study, including assessment of AEs involving the oral cavity
- Changes from baseline in clinical laboratory test results
- Changes from baseline in vital signs and weight
- Changes from baseline indicative of increased suicidal ideation or behavior as assessed by the C-SSRS
- Changes from baseline in MADRS scores
- Changes from baseline in patient-rated sexual function as assessed by the CSFQ-14 in males and in females, described separately

Adverse events will be coded using the latest version of MedDRA and will be summarized overall and by preferred term and system organ class. Adverse events will also be summarized by severity and relationship to study drug. Serious AEs and AEs leading to discontinuation of study drug will also be summarized. Actual values and changes from Baseline for clinical laboratory test results, MADRS scores, CSFQ-14 scores, and vital sign measurements will be summarized at endpoint using descriptive statistics (n, mean, SD, median, minimum, and maximum).

The number of patients with suicidal behaviors, ideations and acts based on the C-SSRS will be tabulated by treatment group and listed.

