## 7. GENERAL ISSUES FOR STATISTICAL ANALYSIS

### 7.1 General Statistical Methodology

Descriptive summaries will be provided where appropriate for each of the primary and secondary variables. In general, tables will summarize data by treatment group and visit.

Baseline characteristic and safety tables will be completed for the Safety Population unless otherwise specified. Efficacy tables will be presented for the mITT Population.

Continuous, quantitative, variable summaries will include the number of participants (N) with non-missing values, mean, standard deviation (SD), median, minimum, and maximum.

Categorical, qualitative, variable summaries will include the frequency and percentage of participants who are in the particular category. In general, the denominator for the percentage calculation will be based upon the total number of participants in the study population for the treatment group unless otherwise specified.

Baseline values are defined as the last non-missing measurement prior to the first dose of study drug. Change from baseline will be defined as the post-baseline visit value minus the baseline value.

ET participants will only be followed if required to monitor an on-going adverse event or other condition.

Participants are not supposed to change study sites; however, should this be necessary to allow a participant to continue in the study, participants will be analyzed under the site where they were initially enrolled.

Study day after first dose is defined as assessment date – first dose date +1. Dates prior to first dose are defined as assessment date – first dose date.

All analyses will be performed using Statistical Analysis System (SAS®) Software version 9.4 or later.

Unless otherwise noted, 95% confidence intervals will be presented for statistical tests.

For the purposes of analyses that include a site covariate, sites that have two or fewer subjects will be pooled into a single site. If there are further problems with model convergence, other small sites causing issues will be included in this pooled site.

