#### 7.1.2 Data Handling for Participants Who Discontinue Study Drug or Withdraw from the Study

Participants who withdraw/drop out from the study will have their ET visit data collected and included in the analysis based on the closest visit window (Week 4, 8 or 12). Visit windows will be assigned by splitting the periods between visits at the midpoint between the visits. If more than one record falls within the window, the one closest to the target date will be used in the analysis, with preference given to the scheduled visits in the case of equidistant visits.

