A Mixed Model Repeated Measures (MMRM) analysis will be performed for the change from baseline in CAPS-5 total score to estimate the treatment difference at Week 12. The model will include all participants in the mITT population, and the dependent variable will be the observed change from baseline in CAPS-5 total score at each post-randomization visit. Covariates in the model will include the fixed categorical effects of treatment, site, sex, and treatment by visit interaction, as well as the continuous fixed covariates of baseline score and baseline score by visit interaction. An unstructured covariance matrix will be used to model the within-subject variance-covariance errors. The Kenward-Roger approximation will be used to estimate the denominator degrees of freedom. Should the unstructured model fail to converge, an autoregressive AR(1) covariance structure will be attempted, then finally compound symmetric should AR(1) not converge.

Missing data for participants in the mITT population will be imputed via multiple imputation (MI) ([Carpenter, 2013](#); [Mallinckrodt, 2013](#)). Ten repeats of the imputation will be performed using Markov Chain Monte Carlo (MCMC) assuming non-monotone missing. Where the study medication was discontinued due to lack of efficacy, lost to follow-up, or to an AE, missing values will be imputed drawing from the baseline values, conditioned on the non-missing post-baseline values, of all participants in the mITT population under the assumption that they are missing not at random (MNAR); covariates will include site and sex. If the study medication was discontinued for any other reason, values will be imputed within treatment group using MI under the assumption that they are missing at random (MAR) with covariates for site, sex, and the CAPS-5 score recorded at each time point (including baseline). The MAR approach will also be applied for sporadic missing values (prior to discontinuation).

The test statistic based upon the least squares (LS) mean treatment difference and associated p-value [REDACTED] will be presented for each stage.

In addition, the least squares means and 95% confidence intervals (CIs) will be calculated for the treatment difference between TNX-102 SL and placebo at each time point.

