#### **10.7 Assessment of Changes in Sexual Function: Changes in Sexual Functioning Questionnaire Short-Form (CSFQ-14)**

The CSFQ-14 ([Keller et al. 2006](#)) is validated scale with internal reliability designed to allow a participant to self-evaluate his or her sexual behaviors or problems in several areas. The CSFQ-14 will be administered at Baseline (Visit 2) and Week 12/ET (Visit 6). It yields a total score, three subscales corresponding to phases of the sexual response cycle (i.e. desire, arousal, orgasm), and five subscales corresponding to important

dimensions of sexual functioning. It is considered a useful scale for assessing sexual side effects of medications. For all items, higher scores reflect higher sexual functioning. For 12 of the 14 items, higher sexual functioning corresponds to greater frequency or enjoyment/pleasure (e.g. 1=never to 5 = every day). For two items (item 10, assessing loss of interest after arousal for women and priapism for men, and item 14, assessing painful orgasm), higher sexual functioning corresponds to lower frequency (e.g. 1=every day to 5=never). Items 10 and 14 are included in the total score but not in any scale score.

Descriptive summaries (mean, SD, median, minimum, and maximum) of actual values and changes from baseline at each assessment time point will be reported.

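### The CSFQ-14 has one post-baseline score per patient, yet the SAP gives it the primary repeated-measures model and spreads early-termination scores over Weeks 4, 8 and 12

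*SAP*

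**What the plan says.** **Schedule.** SAP 10.7, like Protocol 11.3.10, states: "The CSFQ-14 will be administered at Baseline (Visit 2) and Week 12/ET (Visit 6"). The visit lists in Protocol 10.4, 10.5 and 10.5.1 and the table in Appendix 1 agree: the CSFQ-14 is absent at Weeks 4 and 8 and present at Week 12 and at ET. SAP 7.1 adds that "ET participants will only be followed if required to monitor an on-going adverse event or other condition", so a patient with an ET score has no later Week 12 score.

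**Model.** SAP 9.2.1 says the continuous secondary endpoints "will be analyzed using an MMRM model identical to the primary endpoint, however, there will be no multiple imputation applied". The list that follows includes "Changes from baseline in patient-rated Changes in Sexual Functioning Questionnaire Short-Form (CSFQ-14) in males and in females, analyzed separately". It adds that "All visits will be included in the analysis", asks for LS means and p-values at each visit, and names Week 12 as the time point of main interest. SAP 9.1.1 defines the model: "Covariates in the model will include the fixed categorical effects of treatment, site, sex, and treatment by visit interaction", plus baseline and baseline-by-visit. Covariance is unstructured, with AR(1) and then compound symmetry as fallbacks, and Kenward-Roger degrees of freedom. SAP 9.2.1 adapts this for the CGI-I and PGIC, which have no baseline, but not for the CSFQ-14.

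**ET data.** Under SAP 7.1.2, ET data are "included in the analysis based on the closest visit window (Week 4, 8 or 12"), with windows split at the midpoints between visits. No endpoint is exempted.

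**Safety summary.** Protocol 13.5 says that "CSFQ-14 scores, and vital sign measurements will be summarized at endpoint using descriptive statistics". SAP 10.7 summarises the CSFQ-14 at each assessment time point. SAP 10.2 and 10.4 give laboratory values and vital signs a last on-treatment row; 10.7 does not.

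**The concern.** A repeated-measures model needs patients with more than one post-baseline record. For the CSFQ-14 there are none, so the prescribed covariance model and its fallbacks have nothing to work on. The general windowing rule also creates Week 4 and Week 8 visits that the schedule does not contain and fills them only with patients who left early. The SAP then asks for treatment p-values at those visits, which compare subgroups selected after randomization.

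Both documents describe the scale as useful for detecting sexual side effects of drugs, and the protocol collects it even at an ET visit before Day 11, when the CAPS-5 is not taken. Scores gathered so that early leavers are represented would be missing from the Week 12 comparison.

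**Working it through.** The documents give no CSFQ-14 figure to reproduce. The check has five steps.

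1. **Records per patient** (Protocol 10.2.1, 10.4, 10.5, 10.5.1, Appendix 1; SAP 7.1). Baseline: one. Weeks 4 and 8: none scheduled. Then Week 12 or ET, not both. The maximum post-baseline count is 1.

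2. **Windows** (target Days 28, 56 and 84 from Protocol 10.4 and 10.5; midpoint rule from SAP 7.1.2). (28 + 56)/2 = Day 42 and (56 + 84)/2 = Day 70. ET scores up to Day 42 go to Week 4, Days 43-70 to Week 8, and later ones to Week 12.

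3. **Identifiability.** The covariance between two visits is informed only by patients with records at both. An unstructured matrix for three visits has 3 × 4/2 = 6 parameters: three variances and three covariances. I computed the rank of the numerical REML information for a simulated single-sex stratum (assumed: 125 patients, 25% dropout, 12 sites; 19, 14 and 92 records at Weeks 4, 8 and 12). A layout with up to three records per patient, as for the CAPS-5, served as comparison.

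| Structure | Parameters | Rank, one record | Rank, up to three records |
|---|---|---|---|
| Unstructured | 6 | 3 | 6 |
| AR(1) | 2 | 1 | 2 |
| Compound symmetry | 2 | 1 | 2 |

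With one record, the REML criterion is 70.738 whether the correlations are set to 0, 0.4 or 0.8. Adding a constant sex column gives 21 columns of rank 20, so in a single-sex model that term is redundant.

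4. **Weight in the Week 12 contrast.** In the same simulated stratum, the net treatment weight was 0 for Week 4 records, 0 for Week 8 and 1 for Week 12. Sums of absolute weights were 0.09, 0.06 and 2.00. The small non-zero values arise through the shared site effects. The contrast is therefore estimable, and it is essentially a Week 12-only ANCOVA.

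5. **Patients affected.** Dropout rate and timing are assumptions. The share of dropouts' ET scores outside the Week 12 window, for departures on Days 1-83, is:

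| Assumed timing | Week 4 | Week 8 | Week 12 | Outside Week 12 |
|---|---|---|---|---|
| Front-loaded, exp(-d/42) | 73.4% | 20.8% | 5.8% | 94% |
| Uniform | 50.6% | 33.7% | 15.7% | 84% |
| Back-loaded, linear | 25.9% | 45.4% | 28.7% | 71% |
| Back-loaded, quadratic | 13.2% | 47.0% | 39.8% | 60% |
| Back-loaded, cubic | 6.7% | 44.1% | 49.2% | 51% |

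For evenly spread dropout over 84 days the share is 70/84 = 83%. At 15% dropout, 250 × 0.15 × 70/84 = 31.25; at 30%, 250 × 0.30 × 70/84 = 62.5. Hence about 31-62 of 250, both sexes together. Letting timing vary as well, the extremes are 250 × 0.15 × 0.51 = 19.1 and 250 × 0.30 × 0.94 = 70.5. All counts assume that every dropout has an ET score.

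**The case against.** The strongest reply is that SAP 10.7 names a combined Week 12/ET slot at Visit 6. SAP 10.2 and 10.4 repeat that ET data follow 7.1.2, and 10.7 does not. If the slot governs, there is one post-baseline visit, the model collapses to a single-visit ANCOVA, and the 10.7 summary already has its endpoint row. That reading is plausible and may be what was meant. But 7.1.2 is general, nothing in the SAP says 10.7 overrides it, and 9.2.1 still prescribes all visits and p-values at each. The SAP has to choose.

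A second reply is that the protocol synopsis restricts MMRM for secondary endpoints to where it is appropriate. Protocol 13.4.3 and SAP 9.2.1 drop that restriction.

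A third is that pooling ET with Week 12 scores changes the question, since an ET score may follow a short exposure or, as Protocol 10.5.1 allows, a lapse in medication. This stands, and it is why a Week 12-only result belongs beside the pooled one.

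A reader might infer more than the documents support:

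- **That no result could be produced.** The Week 12 mean contrast is estimable. Software may return it with a singularity warning. What fails is the specified covariance and the Kenward-Roger step that depends on it.
- **That the ET scores are discarded.** They would still appear in the Week 4 and Week 8 summaries and in the listings.
- **That the arm with more tolerability dropouts is flattered.** This needs early leavers to have worse CSFQ-14 scores, which nothing in the documents shows.

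**Conclusion.** The point holds as a specification error. Followed as written, SAP 9.2.1 and 7.1.2 apply a model whose within-patient covariance is unidentifiable under all three named structures, include a redundant sex term, and generate Week 4 and Week 8 contrasts among early leavers only. They leave the Week 12 comparison as an ANCOVA that is not specified anywhere. These conclusions follow from the schedule and the SAP text and need no assumption about dropout.

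The size does need one. About 31-62 of 250 patients is an illustration at 15-30% evenly spread dropout. That most dropouts' scores fall outside Week 12 held in every timing pattern tried (51-94%), but it would fail if more than half left after Day 70. The direction of any bias is uncertain.

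The consequence is limited. The CSFQ-14 is outside the fixed sequence, its p-values are nominal, and its safety use is descriptive.

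**What to change.** 1. In SAP 9.2.1, remove the CSFQ-14 from the MMRM list. Specify an ANCOVA of change from baseline at the single Week 12/ET assessment, within each sex, with treatment, baseline CSFQ-14 and pooled site, and no sex or visit terms.
2. In SAP 7.1.2, state that the ET windowing does not apply to the CSFQ-14.
3. In SAP 10.7, show an endpoint (Week 12/ET) row, which also meets the at-endpoint summary in Protocol 13.5, beside a Week 12-only row.
4. Record the change in SAP Section 12, since Protocol 13.4.3 names MMRM for continuous secondary endpoints.

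The cost is SAP wording and one simpler model; no new data are needed. The price of pooling is that ET scores reflect shorter or interrupted exposure, which the Week 12-only row makes visible.

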### **14.3 Appendix 3: Seeds for Imputation:**

The following is the list of seeds to be used for any imputations; they will be used in the order that they appear in the production dataset programming first for primary analyses, then secondaries in the order given in this SAP. In the instance that a sample size increase is needed, the post-interim imputations will use a seed that is 10 greater than the one used on the corresponding pre-interim code. If the list below is insufficient for the number of seeds required, the list will repeat with values 1 greater than those given.

549179445

374794564

446287595

823648962

455675309

884575352

293564245

608574838

795925865

935852284

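### The three label-intended key secondaries are analysed under MAR without imputation, so they target a different estimand from the primary that gates them, and no sensitivity analysis covers the gap

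*SAP*

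**What the plan says.** **Primary.** SAP 9.1.1 splits missing CAPS-5 values by reason for stopping. "Where the study medication was discontinued due to lack of efficacy, lost to follow-up, or to an AE, missing values will be imputed" under a missing-not-at-random (MNAR) assumption, "drawing from the baseline values, conditioned on the non-missing post-baseline values, of all participants in the mITT population". For the remaining reasons: "If the study medication was discontinued for any other reason, values will be imputed within treatment group using MI", assuming MAR. Sporadic gaps before discontinuation are also MAR. SAP 7.1.3 sets up categories and sponsor review of withdrawal reasons because they drive this algorithm.

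**Key secondaries.** SAP 2.2.1 and 7.1.1.1 single out CGI-S, SDS total and PROMIS Sleep Disturbance for labeling. They are tested in that order at the primary's level once the primary succeeds. SAP 9.2.1 analyses them, with all other continuous secondaries, by an "MMRM model identical to the primary endpoint, however, there will be no multiple imputation applied".

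**What that model is.** SAP 9.1.2.3 describes the same step for CAPS-5 under a heading that names it MAR: "This analysis will be identical to the primary analysis, but will not include the MI stage described above". SAP 9.1.2 offers it only as a reference beside two MNAR sensitivity analyses. All three concern CAPS-5 alone.

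**Related text.** SAP 9.2.2 counts missing binary outcomes as non-response. Protocol 13.4.3 specifies MMRM on observed changes for continuous secondaries and mentions no imputation, so the SAP does not depart from the protocol here. SAP Appendix 3 lists imputation seeds to be used "first for primary analyses, then secondaries in the order given in this SAP".

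**The concern.** A likelihood MMRM without imputation treats a patient who stops for an adverse event as if the unseen scores would have followed those of patients in the same arm with a similar observed history. For CAPS-5 the SAP declines to assume this for three classes of dropout and keeps it as a reference analysis. For the three endpoints that carry label claims, it is the only analysis.

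The same patients, leaving for the same adjudicated reasons, are therefore treated one way for the test that opens the gate and another way for the tests behind it. The visible text gives no reason. No planned analysis would show whether a CGI-S, SDS or PROMIS claim depends on MAR. Later data will not settle it either, because SAP 7.1 follows early terminators only where an adverse event or other condition needs monitoring.

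**Working it through.** **1. Is there a figure of the plan to reproduce?** No. The point rests on no stated number. The planned size is 250 (125 per arm), but its effect size, SD, power and dropout inputs are blacked out. Solving backwards at two-sided 0.05, the standardised effect is (1.960 + z_power) × √(2/125): 0.354 at 80% power, 0.410 at 90%, 0.456 at 95%. The 0.40 SD used below is an assumption within that range.

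**2. Who is affected?** Only patients with at least one post-baseline value and none in the Week 12 window.
- Termination before Day 11 collects no CAPS-5, SDS, PROMIS or CGI-S (Protocol 10.5.1). Without another post-baseline value, the patient is in neither analysis.
- Early-termination data go to the nearest visit window, split at midpoints (SAP 7.1.2). The midpoint of Days 56 and 84 is Day 70, so a termination value after that counts as an observed Week 12 value in both analyses.

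**3. Bounding algebra: full return to baseline.** Let m be the placebo improvement, δ the true effect, and dT and dC the shares of drug and placebo patients lost for the three MNAR reasons. If all of them showed zero change, the difference would be

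(1 − dT)(m + δ) − (1 − dC)m, with δ = 0.40.

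- Equal dropout d gives 0.40(1 − d): 0.36, 0.32 and 0.28 at 10%, 20% and 30%.
- 25% drug / 15% placebo: 0.75(1.2) − 0.85(0.8) = 0.22 at m = 0.8; 0.75(1.6) − 0.85(1.2) = 0.18 at m = 1.2.
- 15% drug / 25% placebo: 0.85(1.2) − 0.75(0.8) = 0.42; 0.85(1.6) − 0.75(1.2) = 0.46.
- It equals the MAR value when dC/dT = 1 + δ/m, that is 1.5 at m = 0.8 and 1.33 at m = 1.2. Example at m = 1.2: 0.85(1.6) − 0.80(1.2) = 0.40.

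**4. Simulation of the rule actually written.** SAP 9.1.1 does not set patients to their own baseline. It draws from pooled baseline values given the observed post-baseline values. This was simulated with 125 per arm, 400 runs per scenario, 10 imputations, between-visit correlation 0.6 and random dropout after Week 4 or Week 8, all of it in the MNAR class. Within-arm MAR imputation stood in for the likelihood MMRM. Site, sex and the two-stage combination were left out. Effects are in single-visit SD units. Entries are for m = 0.8 / m = 1.2, with the share of significant runs in brackets.

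| Drug / placebo dropout | MAR (key secondaries now) | Primary's rule |
|---|---|---|
| 10% / 10% | 0.403 / 0.403 (0.975 / 0.958) | 0.381 / 0.379 (0.935 / 0.897) |
| 20% / 20% | 0.411 / 0.407 (0.945 / 0.940) | 0.356 / 0.357 (0.868 / 0.780) |
| 30% / 30% | 0.398 / 0.398 (0.915 / 0.892) | 0.329 / 0.320 (0.713 / 0.620) |
| 25% / 15% | 0.403 / 0.393 (0.943 / 0.930) | 0.254 / 0.206 (0.502 / 0.335) |
| 15% / 25% | 0.395 / 0.398 (0.940 / 0.938) | 0.447 / 0.486 (0.968 / 0.970) |

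The simulation error of a bracketed share is at most √(0.25/400) = 0.025.

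**5. Reading.** MAR returns about 0.40 SD whatever the dropout pattern. The primary's rule moves with the pattern: down with equal dropout, further down when drug loses more, up when placebo clearly loses more.

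**The case against.** Much of the case for the current text stands, and it limits the point.

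- **Type I error.** A reader might infer that the mismatch breaks the fixed sequence. It does not: each test is valid under its own assumption, and nothing is tested until the primary has succeeded under its MNAR handling.
- **Direction.** A reader might infer that MAR always favours the drug. The documents give no dropout rates by arm. The MNAR class pools lack of efficacy and loss to follow-up with adverse events, and lack of efficacy could be commoner on placebo. At 15% drug / 25% placebo the primary's rule is the more favourable.
- **Size.** A reader might take the primary's rule as full return to baseline, helped by the SAP's own shorthand in 9.1.2.1, "imputed values based on the baseline distribution". The conditional draw is only a partial return: at 20% per arm it removes about 10% of the effect, not 20%.
- **Comparability.** A reader might conclude that the primary and key secondaries cannot be read together. SAP 9.1.2.3 already gives a MAR primary that matches the secondary method. What is missing is the reverse: key secondaries under the primary's assumption.
- **Appendix 3.** A reader might see a contradiction with 9.2.1. The appendix reserves seeds for whatever imputations are run and does not say that any secondary will be imputed. The specific text in 9.2.1 governs, so this is a wording repair.

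None of this supplies a reason for the different handling or a sensitivity analysis for the three label endpoints.

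**Conclusion.** The point holds as an unexplained difference in estimand together with a missing sensitivity analysis, confined to CGI-S, SDS total and PROMIS T-score. It should be corrected before unblinding, but it is not an error-rate failure.

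In the illustration, MAR is more favourable than the primary's rule unless such dropout is clearly higher on placebo. With 20% per arm the gap is modest (about 0.40 against 0.36 SD). At 25% drug / 15% placebo it could decide a claim: 0.21 to 0.25 SD, with 34% to 50% of runs significant against 93% to 94% under MAR. At 15% drug / 25% placebo it reverses (0.45 to 0.49 SD). These sizes rest on the assumed effect, placebo improvement, correlation and dropout; only the difference in handling comes from the documents.

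**What to change.** In SAP 9.2.1, except the three key secondaries from the no-imputation rule. Apply the reason-based imputation of 9.1.1 to them, with the same MNAR and MAR classes, and report the MMRM without imputation as supporting, mirroring 9.1.2.3. Leave the other continuous secondaries as planned. At minimum, keep MAR as the main analysis with a stated justification and prespecify the reason-based imputation as a sensitivity analysis for these three before unblinding.

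The text should also:
- say how imputed values are handled on the 1 to 7 CGI-S and on the SDS total when it is prorated from two domains;
- name the analysis set, since 9.2.1 uses an endpoint-specific set while SAP 7.1 and Protocol 13.4.3 refer to mITT;
- align Appendix 3 by naming the secondaries that will use seeds.

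The cost is modest. The three endpoints have baselines and the same post-baseline clinic visits as CAPS-5, the withdrawal reasons are already reviewed, and the imputation method is already specified. What remains is a little programming and the scale rules above. The downside is that key-secondary estimates may be less favourable.
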